	Grade 3 or 4, or recurrent Grade 2	Permanently discontinue		

Immune-related Adverse Event	Toxicity Grade or Conditions (CTCAE v5.0)	Action Taken with Ipilimumab	irAE Management with Corticosteroids and Other Therapies	Monitoring and Follow-up
			Add prophylactic antibiotics for opportunistic infections	
Diarrhea / Colitis	Grade 2	Withhold until symptoms recover to Grade 1; can consider permanently discontinuing	Administer corticosteroids (initial dose of 1–2 mg/kg prednisone or equivalent) followed by taper. Subjects with diarrhea/colitis should be advised to drink liberal quantities of clear fluids. If sufficient oral fluid intake is not feasible, fluid and electrolytes should be substituted via IV infusion.	Monitor subjects for signs and symptoms of enterocolitis (i.e., diarrhea, abdominal pain, blood or mucus in stool with or without fever) and of bowel perforation (i.e., peritoneal signs and ileus). Subjects with Grade \geq 2 diarrhea suspecting colitis should consider GI consultation and performing endoscopy to rule out colitis.
	Grade 3 or 4	Permanently discontinue		
AST / ALT elevation or Increased bilirubin	Grade 2	Withhold	Administer corticosteroids (initial dose of 0.5–1 mg/kg prednisone or equivalent) followed by taper	Monitor with liver function tests (consider weekly or more frequently until liver enzyme value returns to baseline level or is stable)
	Grade 3 or 4	Permanently discontinue	Administer corticosteroids (initial dose of 1–2 mg/kg prednisone or equivalent) followed by taper	
Type 1 diabetes mellitus (T1DM) or Hyperglycemia	Newly onset T1DM or Grade 3 or 4 hyperglycemia associated with evidence of β -cell failure	Withhold until glucose control obtained with reduction to no greater than Grade 1 toxicity	Initiate insulin replacement therapy for subjects with T1DM. Administer antihyperglycemic in subjects with hyperglycemia.	Monitor subjects for hyperglycemia or other signs and symptoms of diabetes

Immune-related Adverse Event	Toxicity Grade or Conditions (CTCAE v5.0)	Action Taken with Ipilimumab	irAE Management with Corticosteroids and Other Therapies	Monitoring and Follow-up
Hypophysitis	Grade 2	Consider holding until stabilized on replacement hormones	Administer corticosteroids and initiate hormonal replacements as clinically indicated	Monitor for signs and symptoms of hypophysitis (including hypopituitarism and adrenal insufficiency)
	Grade 3 or 4	Consider holding until stabilized on replacement hormones or permanently discontinue ^a		
Hyperthyroidism	Grade 2	Continue	Treat with nonselective beta-blockers (e.g., propranolol) or thionamides as appropriate	Monitor for signs and symptoms of thyroid disorders
	Grade 3 or 4	Consider holding until symptoms return to baseline or permanently discontinue ^a		
Hypothyroidism	Grade 2–4	Continue	Initiate thyroid replacement hormones (e.g., levothyroxine or liothyroinine) per standard of care	Monitor for signs and symptoms of thyroid disorders
Nephritis and Renal dysfunction	Grade 2	Withhold	Administer corticosteroids (prednisone 1–2 mg/kg or equivalent) followed by taper	Monitor changes of renal function
	Grade 3 or 4	Permanently discontinue		
Myocarditis	Grade 1 or 2	Withhold, consider discontinuation if Grade 2	Based on severity of AE administer corticosteroids	Ensure adequate evaluation to confirm etiology and/or exclude other causes
	Grade 3 or 4	Permanently discontinue		

Immune-related Adverse Event	Toxicity Grade or Conditions (CTCAE v5.0)	Action Taken with Ipilimumab	irAE Management with Corticosteroids and Other Therapies	Monitoring and Follow-up
All other immune-related AEs	Intolerable/persistent Grade 2	Withhold		
	Grade 3	Withhold or discontinue based on the type of event. Events that require discontinuation include but are not limited to: Guillain-Barre Syndrome, encephalitis	Based on type and severity of AE administer corticosteroids	Ensure adequate evaluation to confirm etiology and/or exclude other causes
	Grade 4 or recurrent Grade 3	Permanently discontinue		

NOTE: For subjects with Grade 3 or 4 immune-related endocrinopathy where withholding of ipilimumab is required, ipilimumab may be resumed when the AE improves to Grade ≤ 2 and is controlled with hormonal replacement therapy or metabolic control is achieved (in the case of T1DM).

AE = adverse event, ALT = alanine aminotransferase, AST = aspartate aminotransferase, CTCAE = Common Terminology Criteria for Adverse Events: GI = gastrointestinal, irAE = immune-related adverse event, IV = intravenous, T1DM = Type 1 diabetes mellitus.

^a Withholding or permanently discontinuing ipilimumab is at the discretion of the investigator or treating physician.

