- For subjects with average Grade 2 or 3 QTcF prolongation at doses of 75 mg or greater (measured at times other than during the up to 6-hour period immediately following an FLX475 dose when a threshold of Grade 3 QTcF prolongation should be used), interrupt treatment with FLX475 until resolution to Grade 0 or 1 or to the pretreatment severity grade, then resume treatment at 50 mg. Subjects with average Grade 2 or 3 QTcF prolongation while at the 50 mg or lower dose level of FLX475 (measured at times other than during the up to 6-hour period immediately following an FLX475 dose when a threshold of Grade 3 QTcF prolongation should be used) should be permanently discontinued from FLX475 treatment (unless it is determined by the investigator, in consultation with the Sponsor's medical monitor, to be in the subject's best interest to continue treatment either at 50 mg or at a reduced dose of 25 mg). Any subjects with observed QTcF prolongation of potential significance should have the ECG repeated for confirmation and electrolytes assessed and replaced as needed prior to action with study drug being taken. Any subjects with observed Grade 4 QTcF prolongation (including symptomatic/serious arrhythmia) should be treated appropriately and permanently discontinued from FLX475 treatment (unless it is later determined by the investigator, in consultation with the Sponsor's medical monitor, to be in the subject's best interest to continue treatment).
- The investigator may interrupt treatment with FLX475 for any other AE considered unacceptable for the individual subject, and treatment may be resumed at the previous lower dose level when resolved to Grade 0 or 1 or to pretreatment severity grade.
- If no lower dose level exists to which the subject may de-escalate, FLX475 should be discontinued.

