Other dose modifications may be acceptable but should be implemented at the investigator's discretion in consultation with the Sponsor's medical monitor, considering the subject's condition and the clinical benefit to the subject of continuing treatment at the current dose. If the subject requires a dose modification for an AE, then FLX475 administration should be interrupted, as necessary (and upon consultation with the Sponsor's medical monitor), until the AE resolves or stabilizes to an acceptable degree (generally to CTCAE Grade 0 or 1 or to pretreatment severity grade). Thereafter, treatment with FLX475 may be reinstated at the previous lower dose level. Subsequent reductions to successively lower dose levels can be made, if needed, as shown in [Table 2](#). More frequent laboratory monitoring may be required. Once the dose of study treatment has been reduced, it may not be increased at a later date without approval from the Sponsor's medical monitor. (Note that AEs known to be associated with ipilimumab may not require interruption or modification of FLX475 dosing.)

Table 2 Dose Modification Guidelines for FLX475-Related Toxicity

Treatment-Related Toxicity ^{a,b}	Management	Dose Adjustment
Grade 1 or Tolerable Grade 2		
	Continue treatment	No change
Intolerable Grade 2^c or Grade 3^{d, e}		
First occurrence	Interrupt FLX475 until resolved to Grade 0–1 or tolerable Grade 2 (or baseline)	Reduce FLX475 dose by 1 level (or if no lower dose level exists, discontinue drug)
Second occurrence (same toxicity or new toxicity)	Interrupt FLX475	Discuss with Sponsor
Grade 4^f: Discontinue Study Treatment		

Note: For grading see CTCAE version 5.0 ([Appendix 1](#)). Collect all CTC grades of adverse events, decreasing and increasing grade.

BMI = body mass index, CTCAE = Common Terminology Criteria for Adverse Events.

- a An interruption of study treatment for more than 21 days will require Sponsor's approval before treatment can be resumed.
- b Initiate optimal medical management for nausea, vomiting, hypothyroidism and/or diarrhea prior to any study treatment interruption or dose reduction.
- c Applicable only to Grade 2 toxicities judged by the subject or physician to be intolerable.
- d For Grade 3 toxicity, investigator will decide the probability of the event being related to 1 or both drugs and as to whether dose modification of either or both drugs is required.

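### Table 4 gives two ipilimumab restart thresholds after Grade 3–4 immune-related T1DM or hyperglycemia; FLX475 has a softer mismatch between Section 10.5.1 and Table 2

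*Protocol*

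**What the plan says.** **Ipilimumab (protocol Section 10.5.2, Table 4).** The trigger for the diabetes row begins "Newly onset T1DM or Grade 3 or 4 hyperglycemia associated with evidence of", the evidence meant being of β-cell failure. Its action is "Withhold until glucose control obtained with reduction to no greater than Grade 1 toxicity". The NOTE beneath the table applies as follows: "For subjects with Grade 3 or 4 immune-related endocrinopathy where withholding of ipilimumab is required". In that case "ipilimumab may be resumed when the AE improves to Grade ≤ 2 and is controlled with hormonal replacement therapy". The NOTE then adds a condition specific to diabetes: "or metabolic control is achieved (in the case of T1DM".

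**FLX475 (protocol Section 10.5.1).** One bullet deals with QTcF prolongation at 75 mg or above: "interrupt treatment with FLX475 until resolution to Grade 0 or 1 or to the pretreatment severity grade". A later bullet lets the investigator interrupt for any other adverse event judged unacceptable for that subject, after which "treatment may be resumed at the previous lower dose level when resolved to Grade 0 or 1 or to pretreatment severity grade". Table 2, for the first occurrence of intolerable Grade 2 or Grade 3 treatment-related toxicity, says "Interrupt FLX475 until resolved to Grade 0–1 or tolerable Grade 2 (or baseline"). Between the bullets and Table 2, a general paragraph asks for interruption until the event has resolved or settled acceptably. It gives Grade 0–1 or the pretreatment grade as the usual mark, not a fixed one. The section introduces all of these rules as guidelines for use beyond Cycle 1.

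**The concern.** A restart threshold is the rule a site applies on the day it decides whether to give drug again. If two current passages set different grades for the same event, two sites can treat the same subject differently and each can point to the protocol.

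The immediate stake is consistent safety management. The secondary stake is interpretation of the safety data. Protocol Section 12.1.8.1 summarizes treatment interruptions, and SAP Section 7.5.1 reports total FLX475 dose and the number of ipilimumab infusions. All three would partly reflect which passage a site had read. For FLX475, the stricter threshold can also lengthen an interruption past 21 days, the point at which Table 2 requires Sponsor approval to resume.

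**Working it through.** The documents state no figure on this point and no calculation was run. The check applies each rule to the same subject.

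**Step 1. Ipilimumab: where the two rules overlap.** The row covers new-onset T1DM with no grade stated, and Grade 3–4 hyperglycemia with β-cell failure. The NOTE covers Grade 3–4 immune-related endocrinopathy for which ipilimumab must be withheld. The overlap is therefore Grade 3–4 events only. The NOTE cannot be set aside as being about other glands, because it names T1DM. Among the endocrine rows of Table 4, the diabetes row is also the only one with an unconditional instruction to withhold: hypophysitis and Grade 3–4 hyperthyroidism say to consider holding, and Grade 2 hyperthyroidism and hypothyroidism say to continue.

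**Step 2. Ipilimumab: apply both rules.**

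| Subject's course | Table 4 row | Table 4 NOTE |
|---|---|---|
| Grade 3–4, now Grade 1, controlled | May restart | May restart |
| Grade 3–4, now Grade 2, metabolic control | Withhold | May restart |
| New-onset T1DM, never reached Grade 3, now Grade 2 | Withhold | Does not apply |

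Only the middle line conflicts. The NOTE's sequence of conditions can be parsed two ways: Grade 2 or lower together with either form of control, or metabolic control alone being enough for T1DM. Neither parsing requires Grade 1, so the conflict does not depend on the parsing.

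**Step 3. FLX475: where the rules overlap.** The bullet covers any other adverse event, related or not. Table 2 covers treatment-related toxicity, and its threshold is for a first occurrence; a second goes to discussion with the Sponsor. QTcF prolongation has its own bullet. If the pretreatment grade was already 2, which inclusion criterion 7 allows for some toxicities, both rules permit restart at Grade 2. The overlap that matters is a first, treatment-related, non-QTcF toxicity with a pretreatment grade below 2.

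**Step 4. FLX475: apply the rules.** Take a related Grade 3 event, absent before treatment, that settles at tolerable Grade 2.

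| Source | Restart at tolerable Grade 2? |
|---|---|
| 10.5.1 bullet for other adverse events | No |
| 10.5.1 general paragraph | Not usually, but not excluded |
| Table 2 | Yes, one dose level lower |

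The bullet and Table 2 both restart at a lower dose level. They differ on the grade.

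**Step 5. Bound on the ipilimumab effect per subject.** At most four doses are planned. An ipilimumab-related event follows at least one of them, so at most 4 − 1 = 3 doses can depend on the restart decision.

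**The case against.** The strongest reply concerns FLX475. The rules there are guidelines to be considered, and the bullet is permissive both about interrupting and about resuming. The general paragraph leaves room for a settled Grade 2, and Sections 10.5, 10.5.1 and 10.8 provide for consultation with the medical monitor. This stands in part: it would be wrong to describe the two passages as opposing mandatory orders. But discretion to depart from a default does not say what the default is, and the bullet itself carries no hedge on the grade.

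For ipilimumab, the NOTE is also permissive, so a site that always waits for Grade 1 breaches neither passage. That is true, but a site relying on the NOTE would restart a subject whom the row keeps off drug. Nor does it help to read the NOTE as an override for Grade 3–4 events. T1DM that never reached Grade 3 would then face a tighter restart grade than T1DM that did, and nothing in the text says that this is intended.

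Three stronger readings are tempting, and the documents do not support them.

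- A reader might infer that every hold or interruption settling at Grade 2 is affected. Steps 1 and 3 show that the overlap is narrower.
- A reader might infer that restarting at the wrong grade counts as an important deviation under SAP Section 7.3.2. Its minimum criteria name wrong treatment or incorrect dose and do not mention the grade at restart. Giving a protocol dose at one grade or another is not plainly an incorrect dose.
- A reader might want to attach a count of subjects. No document gives a rate of these events or of interruptions settling at Grade 2.

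**Conclusion.** The point holds in a narrow form. For ipilimumab, Table 4 contradicts itself for Grade 3–4 immune-related T1DM or hyperglycemia that has improved to Grade 2 with metabolic control. This rests on the words of the row and the NOTE, and on hyperglycemia with β-cell failure counting as endocrinopathy; for T1DM, which the NOTE names, no such assumption is needed. For FLX475 there is a secondary and softer mismatch, limited to the overlap in Step 3, in which the text leaves the default threshold unclear.

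The size is small and cannot be expressed as a number of subjects. No sample size, power or efficacy figure depends on it, and the SAP (Sections 7.4.1 and 7.7) drops efficacy summaries because the study was discontinued early. What remains is consistent subject management wherever this text is in use, and correct reading of holds and interruptions in the safety report. Nothing here bears on which grade is clinically right.

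**What to change.** Reconcile the Table 4 diabetes row with its NOTE, so that a Grade 3–4 event has a single restart threshold for ipilimumab, and word the NOTE so that its conditions can be read only one way. For FLX475, reconcile three places together: the Section 10.5.1 bullet for other adverse events, the general paragraph before Table 2, and Table 2. Changing only the bullet and the table could leave the paragraph as a third wording. The sponsor should choose the grades on clinical grounds.

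The cost is a handful of wording edits, with no change to data collection or analysis. Because the edits affect subject safety, Section 14.1 would route them through an amendment with regulatory submission and ethics approval. Since the study has stopped early, the practical equivalent is a short statement in the clinical study report of how holds and restarts were decided, and correction of the text before it is reused in another protocol.

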10.6 Identity of Investigational Products

The study treatments under evaluation in this study are FLX475 and ipilimumab. Ipilimumab is not considered an investigational product in this study. FLX475 will be provided to sites as open-label supplies by the Sponsor.

10.6.1 *FLX475*

FLX475 is a crystalline non-hydroscopic material that is moderately soluble in water. FLX475 will be supplied as tablets [REDACTED]

[REDACTED]

10.6.2 *Ipilimumab*

Ipilimumab is an IgG1 kappa immunoglobulin with an approximate molecular weight of 148 kDa. Commercial supplies of ipilimumab will be used in this study.

The Yervoy® Package Insert contains specific instructions for the preparation of the ipilimumab infusion and administration of the infusion solution.

10.6.3 *Supply, Packaging, and Labeling of Study Drug*

FLX475 will be provided to the investigational sites by RAPT Therapeutics, Inc. Ipilimumab will not be provided by the Sponsor and will be administered at the site according to its approved use paid for by insurance coverage in patients with unresectable and metastatic melanoma.

FLX475 for oral administration will be provided as tablets containing the active ingredient as well as standard pharmaceutical grade excipients. FLX475 will be packaged in bottles.

FLX475 in all dose strengths, will be labeled in accordance with text that is in full compliance with FDA requirements.

10.6.4 *Storage Conditions*

Bottles containing tablets of FLX475 should be stored at a controlled room temperature, 20–25°C (68–77°F). Study drug should be stored in the container in which it is supplied, in a secured area to which access is limited to appropriate study personnel. FLX475 tablets should be stored protected from light and according to the storage information provided on the label.

Storage of ipilimumab should follow institutional standards and per [Yervoy® Package Insert](#).

10.7 Selection of Doses in the Study

As described in [Section 6.1.4.1](#), a recommended Phase 2 dose of FLX475 of 100 mg PO QD has been selected in the ongoing FLX475-02 study. Dose reductions (e.g. to 50 mg) are

permitted as needed. Subjects will take FLX475 once daily. Each 3-week treatment period is considered to be 1 treatment cycle, based on administration of ipilimumab.

The dose of ipilimumab used in this study, 3 mg/kg mg as an IV infusion Q3W for a maximum of 4 doses, is the approved dosage in unresectable or metastatic melanoma. Additional dosage regimens of 10 mg/kg and 1 mg/kg are also approved in other clinical settings.

10.8 Selection of Dose and Timing for Each Subject

Subjects should maintain a normal diet unless modifications are required to manage an AE such as diarrhea, nausea, or vomiting. Fasting is not required for FLX475 administration.

FLX475 tablets are to be taken with water orally once a day at approximately the same time each day in every 3-week cycle (21 days) from Cycle 1 Day 1 onward.

Ipilimumab will be administered at a dose of 3 mg/kg as a 30- or 90-minute IV infusion (per institutional protocol), Q3W, on Day 1 of each 3-week (21-day) cycle for cycles 1–4, approximately 1 hour after the FLX475 dose and after the 1-hour post-FLX475 dose assessments have been completed.

Dose modifications may be acceptable for toxicity but should be implemented at the investigator's discretion in consultation with the Sponsor's medical monitor after considering the subject's condition and the clinical benefit to the subject of continuing treatment at the current dose.

See [Section 10.5](#) for details pertaining to the guidelines for dose modifications in this study.

10.9 Blinding

The study will not be blinded to the investigator or the subject. However, any independent radiologists reading the tumor assessment images for response/progression, if used, will be blinded per standard procedures.

10.10 Prior and Concomitant Therapy

10.10.1 Recording of Prior and Concomitant Treatments and Procedures

The investigator or qualified designee will review prior medication use, including any protocol-specified washout requirement, and record prior medications taken by the subject within 30 days before the first dose of study treatment. The dates and doses of the most recent CPI administered (e.g. anti-PD-1 or anti-PD-L1 therapy) prior to study entry should be recorded even if beyond 30 days before the first dose of study treatment. Prior antibiotic usage (type, dose, and duration) for up to 6 months prior to study entry should also be recorded, if the information is readily available.

All prior medications (including over-the-counter medications) administered within 30 days before the first dose of study treatment and any concomitant therapy administered to the

subject during the course of the study (starting at the date of informed consent) until 30 days after the final dose of study treatment will be recorded on the appropriate eCRF(s). Additionally, all diagnostic, therapeutic, or surgical procedures relating to malignancy should be recorded. Any medication that is considered necessary for the subject's health and that is not expected to interfere with the evaluation of or interact with the study treatment may be continued during the study. If the concomitant medication/therapy is being administered for a medical condition present at the time of entry into the study, the investigator will record the medical condition on the appropriate eCRF.

10.10.2 Drug-Drug Interactions

FLX475 showed no significant inhibition of CYP1A2, CYP2C9, CYP2C19, CYP2D6 and CYP3A4. In human hepatocytes, FLX475 showed no induction of CYP1A2, CYP2B6, and CYP3A4. As FLX475 did not induce any of these three CYP450 enzymes, and the regulatory elements of these three CYP450 enzymes are also involved in the induction of most drug-metabolizing enzymes, FLX475 is considered unlikely to induce any other drug metabolizing pathways. At clinically relevant doses and exposures in humans, FLX475 is unlikely to inhibit or induce the activity of the major drug metabolizing CYP450 enzymes. Based on its low efflux ratio (1.3) in a Caco-2 cell assay, FLX475 is also unlikely to be affected by inhibitors of drug transporters such as P-gp and BCRP. Refer to the FLX475 Investigator's Brochure for details.

No formal PK drug interaction studies have been conducted between FLX475 and ipilimumab. Ipilimumab is a monoclonal antibody; PK interactions with FLX475 (and vice versa) are not expected.

